#### 4. CMS – NOAC

Superiority Analysis – CMS NOAC					
Number of patients matched	238,234	238,234	238,234	238,234	238,234
Reference	119,117	119,117	119,117	119,117	119,117
Exposure	119,117	119,117	119,117	119,117	119,117
Risk per 1,000 patients	52.5732835	52.5732835	52.5732835	52.5732835	52.5732835
Alpha (2-sided)	0.05	0.05	0.05	0.05	0.05
Desired HR from RCT	0.8	0.7	0.6	0.5	0.4
Number of events expected	12524.7436	12524.7436	12524.7436	12524.7436	12524.7436
Power	1	1	1	1	1

• Stop analyses until balance and final power assessment are reviewed by primary investigators, FDA, and assigned members of advisory board.

Reviewed by PI:	Date reviewed:	
Reviewed by FDA:	Date reviewed:	
Reasons for stopping		
analysis (if required):		

#### 11. Study Confidence and Concerns

Deadline for voting on study confidence and listing concerns: Date votes and concerns are summarized:

- If final feasibility and power analyses are reviewed and approved, proceed to the remaining protocol steps.
- All study team and advisory board members that review this protocol should at this stage provide their level of confidence for the success of the RWD study in the Google Form. This form also provides space for reviewers to list any concerns that they feel may contribute to a failure to replicate the findings of the RCT, including differences in study populations, poor measurement of study variables, or residual confounding. All responses will be kept confidential and individual-level results will only be shared with the individual respondent.
- After the deadline for voting has passed, provide the distribution of responses and summarize all concerns here.

#### 12. Register study protocol on clinicalTrials.gov

Date conducted:

Register the study on clinicalTrials.gov and upload this document.

#### **13. Comparative Analyses**

Aetion report name: Date conducted:

- 13.1 For primary analysis:
- 13.2 For sensitivity analyses:

#### 14. Requested Results

#### 14.1 Table 1: Baseline characteristics before and after adjustment

Variable	Before adjustment		After adjustment			
	Referent	Exposure	Std. diff.	Referent	Exposure	Std. diff.
Number of patients			-			-
Age categories						

#### 14.2 Table 2: Follow-up time

Patient Group	Median Follow-Up Time (Days) [IQR]
Overall Patient Population	
Referent	
Exposure	

### 14.3 Table 3: Censoring events

	Overall	Referent	Exposure
--	---------	----------	----------

#### Effectiveness research with Real World Data to support FDA's regulatory decision making

Outcome		
Death		
Start of an additional exposure		
End of index exposure		
Specified date reached		
End of patient data		
End of patient enrollment		

#### 14.4 Table 4: Results from primary analyses;

Analysis	No. exposed events	No. referent events	Exposed rate	Referent rate	HR (95% CI)
Crude					
Analysis 1					
Analysis 2					

HR, Hazard Ratio; CI, Confidence Interval.

Textu, DETAILS     TEXAL DETAILS     Inclusion       Contraction     EXPOSURE vs. CONPARISON     EXPOSURE vs. CONPARISON       Advatants 5 mg PO, wice daily for 12 months of beatment. A dose reduction to 2.5 mg twice daily will apply 14 paleters three 2.7 dite following FO, once daily for 12 months of treatment. A dose reduction to 2.5 mg twice daily will apply 14 paleters with AF sho are receiving DOAC should have their rend function assessed at baseline and at least annually     Advatant: Advatant: The relief of adjudicated clinically relevant bleeding (CRB) events for the duration of the study: 12 beeding (CRB) weets are defined as and or file study: 12 beeding (CRB) weets are defined as and or file study: 12 beeding (CRB) weets are defined as and or file study: 12 beeding (CRB) weets are defined as and or file study: 12 beeding (CRB) weets are defined as and or file study: 12 beeding (CRB) weets are defined as and clinically relevant beeding (MB) events and clinically relevant for file study: 12 beeding (CRB) weets are defined as and clinically relevant for file study: 12 beeding (CRB) weets are defined as and clinically relevant for file study: 12 beeding (CRB) weets and clinically relevant for file study: 12 beeding (CRB) weets and clinically relevant for file study: 12 beeding (CRB) weets and clinically relevant for file study: 12 beeding (CRB) weets and clinically relevant for file study: 12 beeding (CRB) weets and clinically relevant for matching file study: 12 beeding (CRB) weets and clinically relevant for matching file study: 12 beeding (CRB) weets and clinically relevant for matching file study: 12 beeding (CRB) weets and clinically relevant for matching file study: 12 beeding (CRB) weets and clinically relevant for matching file study: 12 beeding (CRB) weets and clinically relevant for matching file study: 12 beeding (CRB) weets and clinically relevant for matching file study: 12 beeding (CRB)	Can be replicated in claim Using dummy definitions for measuring in claims Can't be measured in claim
Aptabases Smg PO, Wice daily for 12 months of treatment. A dose reduction to 2.5 mg brice daily will apply if patterns met 2 of the following 3 criteria age > 80 years, weight, 60 ag; creatinine > 133 micromotil. vs.       Aptabases Smg PO, Wice daily for 12 months of treatment. A dose reduction to 15 mg daily will apply if patterns with creatinine dealing for 22 months of treatment. A dose reduction to 15 mg daily will apply if patterns with creatinine dealing for 22 months of treatment. A dose reduction to 15 mg daily will apply if patterns with creating dealing for 22 months of treatment. A dose reduction to 15 mg daily will apply if patterns with creating dealing for 22 months of treatment. A dose reduction to 15 mg daily will apply if patterns with creating dealing for 20 months apply data and the attern	Using dummy definitions for measuring in claims Can't be measured in clair sin Elderly h but not important for the analysis .5954
plants meel 2 of the following 3 circuits: age > 80 years, weight, 60 kg; creatine > 133 micromath vs.       Accoban: vs.         vs.       vs.       vs.         vs.       vs.       vs.       vs.         vs.       vs.       vs.       vs.         vs.       vs.       vs.       vs.       vs.         vs.       vs.       vs.       vs.       vs.       vs.         vs.       vs.       vs.       vs.       vs.       vs.       vs.         vs.       vs.       vs.       vs.       vs.       vs.       vs.       vs.       vs.       vs.       vs.       vs.       vs.       vs.       vs.       vs.       vs.       vs.       vs. for measuring in claims Can't be measured in claim is in Elderly Can't be measured in claim th th	for measuring in claims Can't be measured in claim is in Elderly Can't be measured in claim th
with creating clearance < 50 mil/min	Can't be measured in clair s in Elderly th valvular 5954
Image: A start of adjudicated clinically relevant bleeding (CRB) events [Time frame: For the duration of the study: 12; months] (CRB events are defined as the composite of major bleeding (MB) events and clinically relevant non-major bleeding (MB) events and clinically relevant non-major bleeding (SB) in any diagnosis position in an inpatient setting (transfusion codes required for non-critical sites)       Graham D.J. Richman ME. Wern Stroka Bleeding, Str	ke M, et al. s in Elderly th th can't be measured in clair can't be measured in clair but not important for the analysis .5954 

Image: Inclusion according to Canadian       Inclusion criteria       Image: Inclusion criteria       Prescribing guidelines for AF in Ca         Image: Confirmed new diagnosis of AF on ECG with an indication to start anticoagulation according to Canadian       Measured [-180, 0] in any diagnosis position in either an inpatient or outpatient care setting       Prescribing guidelines for AF in Ca         Image: Confirmed new diagnosis of AF on ECG with an indication to start anticoagulation according to Canadian       Atrial fibrillation (Non-Valvular)       Integrite case adaption (Non-Valvular) </td 	Image: Confirmed new diagnosis of AF on ECG with an indication to start anticoagulation according to Canadian       Measured [-180, 0] in any diagnosis position in either an inpatient or outpatient care setting       Prescribing guidelines for AF in CA         Cardiovascular Society guidelines       Atrial fibrillation (Non-Valvular)       https://ccs.ca/appluploads/2020/         ICD-9 Diagnosis: 427.31       ICD-10 Diagnosis: 427.31       icd-10 Diagnosis: 148.0, 148.1, 148.2, 148.91         Age >= 18 years       Age >= 18       Age >= 18       EXCLUSION CRITERIA       Image: Additional Construction of thereapeutic anticoagulation       Image: Additional Construction of thereapeutic anticoagulation of the construction of thereapeutic anticoagulation       Image: Additional Construction of thereapeutic a	
Confirmed new diagnosis of AF on ECG with an indication to start anticoagulation according to Canadian       Atrial fibrillation (Non-Valvular) (CD-9 Diagnosis: 427.31 (CD-9 Diagnosis: 427.31)       https://cos.acaapulupioads/2020// 018_PG_EN_web.pdf         2       Age >= 18 years       Age >= 18 years       Age >= 10, 00, 00, 00, 00, 00, 00, 00, 00, 00,	
EXCLUSION CRITERIA       Image: A roly beals       EXCLUSION CRITERIA       Image: A roly beals       Image: A roly b	AF_GUI_2
Have received >72 hours of thereapeutic anticoagulation       Measured [- 180, 0] in prescription claims         Use of Anticoagulants:       Adeparin Sodium, Porcine, Argatroban in 0.9% Sodium Chloride, Argatroban in Sodium, Chloride, Iso-osmotic, Bivalirudin, Dabigatran Etexilate Mesylate, Dalteparin Sodium Porcine,	
Have received >72 hours of thereapeutic anticoagulation Use of Anticoagulants: Adeparin Sodium, Porcine, Argatroban in 0.9% Sodium Chloride, Argatroban in Sodium Chloride, Iso-osmotic, Bivalirudin, Dabigatran Etexilate Mesylate, Dalteparin Sodium Porcine,	
Heparin Sodium Porcine/Dextrose (5% in water or 5% in water/PF), Heparin Sodium, Program Sodium Porcine, and Warfarin Sodium	
2       Creatine clearance < 15 ml/min calculated with the Cockcroft-Gault formula	
Any contradiction for anticoagulation with apixaban or rivaroxaban as determined by the treating physician such as, but not limited to one of the following:	
Mesaured [-180, 0] in any diagnosis position and in an inpatient setting (transfusion codes required for non-critical sites)	
Maior Bleeding See "Major Bleeding" Sheet	
Active Bleeding     Measured [-180,0] in any diagnosis position in an inpatient setting (transfusion codes not required for non-critical sites)     Clinically Relevant Non-Major Bleeding Events	
See "CRNM Bleeds Sheet"	
Measuered [-180, 0] in any diagnosis position in an inpatient or oupatient setting:           DVT           ICD-9 Diagnosis: 451.1x, 451.2x, 451.81, 451.9x, 453.1x, 453.2x, 453.8x, 453.9x, 453.40, 453.41, 453.42, 453.0           ICD-10 Diagnosis: 180.1x, 180.2, 180.3, 180.9, 182.0, 182.1, 182.2x (except 182.21), 182.4x, 182.6x, 182.80, 182.90, 181.A1x, 182.E1x, 182.C1x	
2) Other Indication for anticoagulation (e.g. mechanical valves, venous thromosis)       PE         ICD-9 Diagnosis:       415.1, 415.10, 415.11, 415.12, 415.13, 415.5, 415.16, 417.17, 415.19, 41	
Prosthetic Heart Valve ICD-9 Diagnosis: V43.3 ICD-10 Diagnosis: Z95.2	

1

	Measured [-180, 0] in prescription claims	
3) Dual Antiplatelet Use	Use of Antiplaelets Any of the following: cilostazol, dipyridamole, ticlopidine HCl, aspirin, clopidogrel bisulfate, prasugrel HCl, ticagerlor, aspirin/dipyridamole, ezetimibe	
4) Known liver disease with coagulopathy	Measured [-180,0] in any diagnosis position in an inpatient or outpatient setting Significant Liver Disease ICD-9 Diagnosis: 070 xx, 570 xx, 573 xx, 456 0x, 456 2x, 576 8x, 782 4x, 789 5x ICD-10 Diagnosis: 071 xx, 570 xx, 573 xx, 456 0x, 456 2x, 576 8x, 782 4x, 789 5x ICD-10 Diagnosis: 071 x, 576 6, K76 89, B19.0, B19.9, I85.11, K71.10, K71.0, K71.2, K71.3, K71.51, K72.01, K72.10, K73.9, K74.3, K74.69, K75.2, K75.81, K75.89, K76.0 K76.1, K76.3, K76.6, K76.89, B19.0, B19.9, I85.11, K71.11, K71.7, K71.9, K72.11, K74.1, K74.4, K74.5, K75.3, K76.7, K87, R18.8, B15.9, B16.0, B16.2, B16.9, B18.0, B18.9, B19.10, B19.11, K70.10, K70.41, K71.4, K71.50, K72.91, K74.0, K74.2, K74.60, K75.1, K75.2, K76.81, K83.8, R17, B15.0, B19.21, B25.1, I85.00, K70.0, K70.0, K70.01, K70.2, K70.9, K72.00, K72.00, K73.2, K75.8, K75.0, K76.9, R18.0, B17.0, B17.0, B17.8, B18.1, B19.20, I85.01, I85.10, K70.30, K70.31, K70.40, K71.6, K71.8, K73.0, K73.2, K75.4, K75.9, K76.4, K76.5, K77, K83.5 ICD-9 Procedure: 39, X, 42.91 ICD-10 Procedure: See "Liver Bypass" Sheet Coaguionativ	
	10D-9 Diagnosis: 286, 286.1, 286.4, 286.5, 286.52, 286.53, 286.59, 287.5, 286.0, 286.2, 286.3, 286.6, 286.7, 286.9, 287.1, 287.3, 287.4 10D-10 Dignosis: D67, D68, D68.1, D68.2, D68.3, D68.31, D68.311, D68.318, D68.4, D68.52, D68.61, D68.69, D68.8, D69.41, D69.49, D69.51, D69.59, D65, D66, D68.0, D68.312, D68.32, D68.35, D68.51, D68.59, D68.51, D68.50, D68.40, D69.41, D69.42, D69.51, D69.50, D68.51, D69.59, D65, D66, D68.00, D68.312, D68.32, D68.35, D68.51, D68.55, D68.51, D68.62, D68.61, D69.42, D69.42, D69.42, D69.5, D69.6	
5)Use of contraindicated medications (strong inducers/inhibitors of CYP 3A4/5, P-glycoprotein)	Measured [-180, 0] in prescription claims Strong CYP3A4 Inhibitors/Inducers Inhibitors: Keloconazole, itraconazole, voriconazole, telithromycin, clarithromycin, nefazodone, ritonavir, saquinavir, nelfinavir, indinavir, atazanavir Inducers: Rifampin, rifampicin/rifampin, phenytoin, carbamazepine P-go Inhibitors/Inducers cobicistat, conivaptan, tipranavir	https://depts.washington.edu/anticoag/home/ content/apixaban
6) Promannu	Measured [-180, 0] in any diagnosis position and inpatient and outpatient care setting  Pregnancy Construction	
7) Active malignancy, defined as a) diagnosed with cancer within the past 6 months; or b) recurrent, regionally	Measured [-180, 0] in any diagnosis position in an inpatient or outpatient setting Cancer I CD-9 Diagnosis : 140.x-209.x (except 209.4x, 209.5x, 209.6x) I CD-10 Diagnosis : C00.x-C96, D45	
8) Weight > 120 kg	Measured [-180,0] in any diagnosis position in an inpatient or outpatient setting:           Brypass Surgery           ILCD-9 Encodure:         343842, 52082, 433644, 43645, 43770, 43843, 43845, 43846, 43847           ICD-9 Procedure:         00160JB, 00160KL, 0016029, 00164JL, 001687L, 00168JB, 00168Z9, 00168Z1, 00190ZA, 00194J9, 00194K9, 00194ZA, 00198K9, 00198ZA, 00140ZB, 00140ZB, 00140ZB, 00140ZB, 00140ZB, 00146XA, 00148KB, 00164KD, 00160ZL, 00166ZL, 00190ZA, 00147B, 00134JA, 00144KD, 00148KB, 00164KD, 00160ZL, 00166ZZ, 00196ZZ, 00064ZZ, 00196ZZ, 00196ZZ, 00196ZZ, 00166ZZ, 00166ZZ, 00166ZZ, 00166ZZ, 00166ZZ, 00146Z, 00146ZB, 00160ZL, 00164ZD, 00164ZD, 00146ZB, 00146XD, 00146ZB, 00146ZD, 00164ZD, 00146ZD, 001	
	5)Use of contraindicated medications (strong inducers/inhibitors of CYP 3A4/5, P-glycoprotein) 6) Pregnancy 7) Active malignancy, defined as a) diagnosed with cancer within the past 6 months; or b) recurrent, regionally advanced or metastatic disease; or c) currently receiving treatment or have received any treatment for cancer during	1) Deal Adaptability Deal       Marked Head Streams       Marked Head St

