#### 5. Cohort Identification

#### 5.1 Cohort Summary

An active-comparator, new-user design, propensity score matched, cohort study will be applied to compare patients that received apixaban vs. rivaroxaban. Patients will enter the cohort upon initiation of apixaban or rivaroxaban after a 180 day washout without anticoagulant exposure. They will be required to have a diagnosis code indicating non-valvular atrial fibrillation in the prior 180 days, and be age 18 or older on the date of initiation of therapy. Subjects will be excluded if they have had any indication of stage IV or V CKD, ESRD, an active bleeding episode, cancer, obesity, liver disease, or another indication for long-term anticoagulation, such as hospitalization for DVT or PE, in the prior 180 days. Patients will also be excluded if they have used any contraindicated medications in the prior 180 days or had an indication for atrial fibrillation that was not non-valvular. All patients were required to have continuous enrollment for 180 days prior to cohort entry to ensure incident use of the study drugs.

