#### 5.3 Flowchart of the study cohort assembly For Apixaban vs. Rivaroxaban

	0	ptum CDM	IBM® M	arketScan®	CMS - NOAC	
	Less Excluded Patients	Remaining Patients	Less Excluded Patients	Remaining Patients	Less Excluded Patients	Remaining Patients
All patients in our database		81,796,156		205,537,714		6,886,908
Patients with Apixaban/Rivaroxaban [measured between Dec 28, 2012 and June 30, 2020.]		856,974		685,749		2,232,416
Excluded due to insufficient enrollment [-180, 0]	-118,628 (14%)	738,346	-54,038 (8%)	631,711	-373,136 (17%)	1,859,280
After wash-out for prior use of reference (Rivaroxaban) [-180, -1]	-206,560 (28%)	531,786	-211,703 (34%)	420,008	-601,148 (32%)	1,258,132
After wash-out for prior use of exposure (Apixaban) [-180, -1]	-278,943 (52%)	252,843	-170,997 (41%)	249,011	-549,695 (44%)	708,437
Excluded because patient qualified in >1 exposure category	-13 (<1%)	252,830	-24 (<1%)	248,987	-54 (<1%)	708,383
Exclusion of Missing Age [-180, 0]	-7 (<1%)	252,823	-0 (<1%)	248,987	-151 (<1%)	708,232
Exclusion of Gender (Exclude Missing Values) [start of all available data, 0]	-17 (<1%)	252,806	-0 (<1%)	248,987		
Inclusion of Age >= 18 [0,0]	-170 (<1%)	252,636	-415 (<1%)	248,572		
Inclusion of Non-Valvular A-fib [- 180,0]	-104,252 (41%)	148,384	-132,025 (53%)	116,547	-264,650 (37%)	443,581
Exclusion of Anticoagulant Use [- 180, 0]	-7,414 (5%)	140,970	-6,140 (5%)	110,407	-34,042 (8%)	409,539
Exclusion of CKD Stage 4/5 or ESRD [-180,0]	-2,876 (2%)	138,094	-994 (<1%)	109,413	-7,617 (2%)	401,922
Exclusion of Dialysis or Renal Transplant) [-180, 0]	-158 (<1%)	137,936	-119 (<1%)	109,294	-421 (<1%)	401,501

Exclusion of Bleeding History [-180, 0]	-2,721 (2%)	135,215	-3,332 (3%)	105,962	-23,500 (6%)	378,001
Exclusion of Cancer [-180,0]	-5,556 (4%)	129,659	-3,177 (3%)	102,785	-14,538 (4%)	363,463
Exclusion of Weight > 120 kg [-180, 0]	-6,963 (5%)	122,696	-3,322 (3%)	99,463	-10,521 (3%)	352,942
Exclusion of Significant Liver Disease [-180, 0]	-1,781 (1%)	120,915	-892 (<1%)	98,571	-3,233 (<1%)	349,709
Exclusion of Use of Contraindicated Medications [-180, 0]	-693 (<1%)	120,222	-596 (<1%)	97,975	-2,762 (<1%)	346,947
Exclusion of Dual Antiplatelet Therapy [-180,0]	-3,219 (3%)	117,003	-2,642 (3%)	95,333	-9,829 (3%)	337,118
Exclusion of Other Heart Conditions [-180,0]	-3,603 (3%)	113,400	-3,056 (3%)	92,277	-7,962 (2%)	329,156
Exclusion of Other Indication of Long-Term Anticoagulation [-180, 0]	-489 (<1%)	112,911	-293 (<1%)	91,984	-1,447 (<1%)	327,709

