532.6 - CHRONIC OR UNSPECIFIED DUODENAL ULCER WITH HEMORRHAGE AND PERFORATION 532.60 - CHRONIC OR UNSPECIFIED DUODENAL ULCER WITH HEMORRHAGE AND PERFORATION WITHOUT OBSTRUCTION 532.7 - CHRONIC DUODENAL ULCER WITHOUT MENTION OF HEMORRHAGE OR PERFORATION 532.9 - DUODENAL ULCER UNSPECIFIED AS ACUTE OR CHRONIC WITHOUT MENTION OF HEMORRHAGE OR PERFORATION 533.21 - ACUTE PEPTIC ULCER OF UNSPECIFIED SITE WITH HEMORRHAGE AND PERFORATION WITH OBSTRUCTION 533.4 - CHRONIC OR UNSPECIFIED PEPTIC ULCER OF UNSPECIFIED SITE WITH HEMORRHAGE 533.40 - CHRONIC OR UNSPECIFIED PEPTIC ULCER OF UNSPECIFIED SITE WITH HEMORRHAGE WITHOUT OBSTRUCTION 533.41 - CHRONIC OR UNSPECIFIED PEPTIC ULCER OF UNSPECIFIED SITE WITH HEMORRHAGE WITH OBSTRUCTION 533.5 - CHRONIC OR UNSPECIFIED PEPTIC ULCER OF UNSPECIFIED SITE WITH PERFORATION 533.61 - CHRONIC OR UNSPECIFIED PEPTIC ULCER OF UNSPECIFIED SITE WITH HEMORRHAGE AND PERFORATION WITH OBSTRUCTION 533.9 - PEPTIC ULCER OF UNSPECIFIED SITE UNSPECIFIED AS ACUTE OR CHRONIC WITHOUT MENTION OF HEMORRHAGE OR PERFORATION 534.0 - ACUTE GASTROJEJUNAL ULCER WITH HEMORRHAGE 534.1 - ACUTE GASTROJEJUNAL ULCER WITH PERFORATION 534.2 - ACUTE GASTROJEJUNAL ULCER WITH HEMORRHAGE AND PERFORATION 534,21 - ACUTE GASTROJEJUNAL ULCER WITH HEMORRHAGE AND PERFORATION WITH OBSTRUCTION 534.4 - CHRONIC OR UNSPECIFIED GASTROJEJUNAL ULCER WITH HEMORRHAGE 534.5 - CHRONIC OR UNSPECIFIED GASTROJEJUNAL ULCER WITH PERFORATION 534.6 - CHRONIC OR UNSPECIFIED GASTROJEJUNAL ULCER WITH HEMORRHAGE AND PERFORATION 534.60 - CHRONIC OR UNSPECIFIED GASTROJEJUNAL ULCER WITH HEMORRHAGE AND PERFORATION WITHOUT OBSTRUCTION 535.11 - ATROPHIC GASTRITIS WITH HEMORRHAGE 535.30 - ALCOHOLIC GASTRITIS (WITHOUT HEMORRHAGE) 535.50 - UNSPECIFIED GASTRITIS AND GASTRODUODENITIS (WITHOUT HEMORRHAGE) 535.51 - UNSPECIFIED GASTRITIS AND GASTRODUODENITIS WITH HEMORRHAGE 535.60 - DUODENITIS (WITHOUT HEMORRHAGE) 535.61 - DUODENITIS WITH HEMORRHAGE 537.83 - ANGIODYSPLASIA OF STOMACH AND DUODENUM WITH HEMORRHAGE 562.02 - DIVERTICULOSIS OF SMALL INTESTINE WITH HEMORRHAGE 562.10 - DIVERTICULOSIS OF COLON (WITHOUT HEMORRHAGE) 562.12 - DIVERTICULOSIS OF COLON WITH HEMORRHAGE 569.3 - HEMORRHAGE OF RECTUM AND ANUS 623.8 - OTHER SPECIFIED NONINFLAMMATORY DISORDERS OF VAGINA 626.8 - OTHER DISORDERS OF MENSTRUATION AND OTHER ABNORMAL BLEEDING FROM FEMALE GENITAL TRACT 786.3 - HEMOPTYSIS 786.30 - HEMOPTYSIS UNSPECIFIED 786.39 - OTHER HEMOPTYSIS 285.9 - ANEMIA UNSPECIFIED 790.92 - ABNORMAL COAGULATION PROFILE 363.63 - CHOROIDAL RUPTURE 626.2 - EXCESSIVE OR FREQUENT MENSTRUATION 372.72 - CONJUNCTIVAL HEMORRHAGE

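### The active-bleeding exclusion is applied as a 180-day inpatient code history that includes non-bleeding codes, so patients with no bleed can be removed under a trial-matched criterion

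*Combined protocol and SAP*

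**What the plan says.** Three places describe this exclusion, and they do not agree.

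- **Section 5.1 (Cohort Summary):** "Subjects will be excluded if they have had any indication of stage IV or V CKD, ESRD, an active bleeding episode", followed by other conditions. The sentence closes with a look-back of 180 days.
- **Section 5.3 (flowchart):** the step is labelled "Exclusion of Bleeding History [-180, 0"].
- **Appendix A, exclusion criteria, item 1 (Active Bleeding):** the item sits under an open parent clause, "Any contradiction for anticoagulation with apixaban or rivaroxaban as determined by the treating physician such as, but not limited to one of the following". Two claims definitions follow, both over [-180, 0]. The Major Bleeding arm looks for a code "in any diagnosis position and in an inpatient setting (transfusion codes required for non-critical sites"). The CRNM arm looks for a code "in any diagnosis position in an inpatient setting (transfusion codes not required for non-critical sites").

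The CRNM sheet that supplies the second arm includes "562.10 - DIVERTICULOSIS OF COLON (WITHOUT HEMORRHAGE"). It also lists several gastritis codes described as without hemorrhage, reflux esophagitis (530.11, K21.0) and unspecified anemia (285.9, D64.9). Appendix A uses the same two sheets to define the primary outcome.

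Section 5.2.2 states that the criteria were adapted to stay close to the trial. No passage explains why active bleeding became a 180-day code history. The sensitivity-analysis entry in Section 13.2 is blank.

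**The concern.** Active bleeding and bleeding history are different criteria. A bleed that resolved five months before cohort entry is history. A reflux or diverticulosis code in a secondary position on an earlier admission is neither. Under the CRNM arm either one is enough to exclude, because no transfusion code is needed and any diagnosis position counts.

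The study compares bleeding under two anticoagulants in a population meant to resemble the trial's. This exclusion selects on the same code lists that define the outcome, so it acts on baseline bleeding risk in a way the trial criterion, as transcribed, may not. If the claims result later differs from the trial's, no planned analysis would show whether this rule contributed.

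**Working it through.** **1. Reproduce the flowchart step (Section 5.3).** Remaining = entering − removed.

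| Database | Entering | Removed | Remaining | Share removed |
|---|---|---|---|---|
| Optum | 137,936 | 2,721 | 135,215 | 2.0% |
| MarketScan | 109,294 | 3,332 | 105,962 | 3.0% |
| CMS | 401,501 | 23,500 | 378,001 | 5.9% |
| Sum | 648,731 | 29,553 | 619,178 | 4.6% |

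Each remaining count matches the flowchart. The sums are not printed in the protocol: 2,721 + 3,332 + 23,500 = 29,553, and 29,553 / 648,731 = 4.56%. CMS supplies 23,500 / 29,553 = 79.5% of the removals. In CMS this is the largest clinical exclusion after prior anticoagulant use (34,042). In Optum it is smaller than weight (6,963), cancer (5,556), other heart conditions (3,603), dual antiplatelet use (3,219) and CKD stage 4/5 or ESRD (2,876).

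**2. What the rule requires.** The Major arm needs a transfusion code for non-critical sites, but the CRNM arm does not. Many of the non-critical codes on the Major sheet reappear on the CRNM sheet, diverticulosis of the colon without hemorrhage among them. For those codes the transfusion condition therefore has no effect: one inpatient code in [-180, 0] excludes.

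**3. How many patients a narrower rule would restore.** The documents do not divide the 29,553 into bleeding present at cohort entry, earlier bleeding, and non-bleeding codes only. At this step the number restored lies anywhere from 0 to 29,553.

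For an upper limit on the final cohort, assume restored patients would meet later exclusions at the same rate as those retained:

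- Optum: 111,950 / 135,215 = 82.8%; 2,721 × 0.828 ≈ 2,253
- MarketScan: 91,660 / 105,962 = 86.5%; 3,332 × 0.865 ≈ 2,882
- CMS: 325,926 / 378,001 = 86.2%; 23,500 × 0.862 ≈ 20,263 (unrounded ratio)

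The total is about 25,400. The final cohort would grow from 529,536 to at most about 554,900, and the restored patients would make up at most 4.6% of it.

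**4. Power is not the issue.** The lowest final power at a hazard ratio of 0.8 is Optum's 0.98409 (Section 10). With 1,354.77 events, two-sided alpha 0.05 and 1:1 matching, Schoenfeld's formula gives z = √(1,354.77 / 4) × ln(1 / 0.8) − 1.960 = 18.404 × 0.22314 − 1.960 = 2.147. This is a power of 0.984, as stated.

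**The case against.** The strongest defence has four parts.

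**The trial clause is open.** Active bleeding is one example under the treating physician's judgement, so a physician could also keep a recently resolved bleed out of the trial. This stands. A reader might infer that the trial excludes only active bleeding; the transcribed clause does not say so. Openness does not cover the code list, however: a reflux or diverticulosis code is not evidence of a contraindication to anticoagulation.

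**The window is disclosed and uniform.** Section 5.1 states 180 days, and the other clinical exclusions use [-180, 0] too. Appendix A's key also admits proxy definitions, although the extracted text does not show which rows carry that flag. This answers any charge of concealment. It leaves the conflict between an active episode and a history, and the non-bleeding codes.

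**The rule may work as a washout.** Because exclusion and outcome share code sheets, removing earlier codes limits the counting of old bleeds as new events. This is a legitimate purpose, though the protocol does not state it, and it is a good reason not to shorten the primary window outright. The documents also offer no basis for any particular shorter window.

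**No bias in the comparison is shown.** The rule applies identically to both drugs before matching. This stands as well.

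**Conclusion.** The point holds as a mismatch between a named criterion and the rule that implements it. As written, the rule can remove patients with no bleeding under an exclusion labelled active bleeding, in a study that aims to stay close to the trial's eligibility.

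The step removes 29,553 patients (4.6%). A reader might take this as a count of bleeding-prone patients whom the trial would have enrolled. It is only an upper bound. It includes patients bleeding at or near cohort entry, whom the trial also excludes, and some whom later steps such as cancer, liver disease or coagulopathy would remove. Those removed for a non-bleeding code alone need not be bleeding-prone.

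Three further inferences lack support. Nothing splits the removals by where atrial fibrillation was diagnosed, so the rule cannot be said to fall mainly on patients diagnosed in hospital. No trial bleeding rate is given, so the cohort cannot be shown to be at lower risk than the trial's. The direction and size of any effect on the hazard ratio are unknown.

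The change is worth making before outcome results are seen; the comparative analyses in Section 13 carry no date. The conclusion rests on the appendix as transcribed and on the code sheets being applied as listed.

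**What to change.** 1. Restrict exclusion 1 to codes on the Major and CRNM sheets that denote bleeding. Drop codes that state no hemorrhage, and non-specific ones such as unspecified anemia and reflux esophagitis.
2. Reconcile Section 5.1, the flowchart label and Appendix A item 1, so that all three say whether the criterion is an active episode or a history. If the 180-day window is meant as an outcome washout, say so and keep it as primary.
3. Pre-specify in Section 13.2 a sensitivity analysis that excludes only bleeding coded in a stay overlapping, or ending shortly before, cohort entry. The study team should set and justify the window length. In that analysis, add inpatient bleeding earlier in the 180 days as a propensity-score covariate, and require outcome events to come from a new admission after day 0.
4. Report how many patients the present rule removes for non-bleeding codes alone, and how many for bleeding at or near cohort entry. This replaces the 0 to 29,553 range with actual counts.

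**Cost.** A code-list edit, one covariate and one additional analysis; cohort counts, matching and balance must be rerun. In the sensitivity analysis some old bleeds may be re-coded on a later stay and counted as new, and the new-admission rule only partly prevents this. Because the outcome uses the same sheets, patients restored after a non-bleeding code could be counted as events if that code recurs, so the outcome list needs checking alongside the exclusion list.
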